2.0 BACKGROUND AND RATIONALE

2.1 Prostate Cancer: Current Standard of Care in Treatment

Prostate cancer is the most common non-cutaneous cancer and the second-leading cause of cancer mortality in American men, accounting for 25% (192,280) of new cancer diagnoses and 9% (27,360) of male cancer deaths(3). Clinically localized prostate cancer accounts for the vast majority of new cancer diagnoses, with an estimated 91% of new cases diagnosed at local or regional stages(3). Traditional treatment options for localized disease vary widely, from watchful waiting or active surveillance to aggressive treatment with surgery, radiation therapy, or brachytherapy. Active surveillance is considered the standard-of-care for low grade (e.g. Gleason score 3+3=6) prostate cancers and even some intermediate risk cancers. On active surveillance, patients with long life expectancy who develop a component of high Gleason grade cancer (i.e. Gleason grade 4 or 5) are recommended to have definitive local therapy such as prostatectomy or radiation. While aggressive therapies such as surgery and radiation do offer the opportunity for cure, they are fraught with side effects that can significantly affect quality of life, including erectile dysfunction, urinary incontinence, and bowel dysfunction(4-7). Even recent advances in robotic surgery and radiation techniques have not appeared to significantly reduce the long-term morbidities of definitive local therapy.

2.2 HIFU: Historical Background and FDA Approval

High-Intensity Focused Ultrasound (HIFU) is a noninvasive therapy that precisely delivers ablative ultrasonic energy to deep tissues through skin and mucosa, allowing for transrectal focal ablation of prostate cancers. While the mainstays of therapy for clinically localized prostate cancer induce significant morbidity such as urinary incontinence, erectile dysfunction, and bowel dysfunction due to bystander effects of whole-gland treatment, HIFU permits focal destruction of prostate cancers by ablating either half of the prostate gland or only the tumor itself; these approaches have the potential to minimize morbidities associated with whole-gland treatment and thereby maximize quality of life. HIFU treatment (primarily hemigland and whole-gland) has been used extensively over the last fifteen years in Europe, Canada, and Mexico, and there are numerous articles describing its safety and effectiveness for this application in the Urology literature.

While HIFU therapy has a long track record abroad, it has only recently been approved for prostate ablation in the US. In October 2015, the FDA gave de novo clearance to the Sonablate 450 HIFU platform (manufactured by SonaCare Medical) for the ablation of prostate tissue, making it the first to be approved for this indication in the US. In November 2015, the Ablatherm HIFU platform (manufactured by EDAP TM SA) was given 510(k) clearance for the same indication. While the approvals for these devices do not specifically mention application to prostate cancer, academic and industry leaders are hailing this technology as a major advance for focal prostate therapy, hinting that this technology can avoid the morbidities of surgery for prostate cancer. Local academic centers have already begun to use and market this technology.

2.3 HIFU: International Experience with Prostate Cancer Treatment

HIFU therapy has been a mainstay of prostate cancer care in Europe, Canada, and Mexico for the last fifteen years, and cancer control and side effect outcomes have been very promising. A review of the randomized clinical trials, meta-analyses, and systematic reviews reporting on efficacy and safety of HIFU as primary treatment was recently reported, though this review included a mixed population with regard to tumor mix and ablation zone (whole-gland and hemigland). 5-year disease free survival rates were 61–95%. Common complications associated with HIFU were urinary retention (<1–20%), UTI (2–48%), stress urinary incontinence of any degree (<1–34%), and erectile dysfunction (20–86%). Rare complications included recto-urethral fistula (<2%), bladder neck stenosis, urethral stricture, perineal pain, urinary obstruction, epididymitis, and prostatitis. The largest institutional series of hemigland HIFU for low- (25%) and intermediate-risk (75%) prostate cancers suggested even better results, with return of erectile function for penetrative sex in 95% of men, 90% pad-free and leak-free continent, and 89% had no histological evidence of cancer at 6 months. 89% of men reached the trifecta status of pad-free, leak-free continence, erections sufficient for intercourse, and cancer control at 12 months.(8) True focal therapy is in a nascent stage of development, but early results are similar to hemigland treatment. In a prospective study of 42 men with low- and intermediate-risk cancer at University College London, 95% (95% CI 83–99%) were cancer free on biopsy at 12 months and 84% (95% CI 66–95%) reached trifecta status.(9) These results, though admittedly in highly selected populations, are clear improvements on cancer control and quality of life outcomes in modern surgical and radiation cohorts.

2.5 High-Resolution Prostate MRI (hrMRI)

Over the last several years, our group at Cedars-Sinai has developed technology to improve resolution of standard mpMRI, allowing for improved detection of smaller tumors. (1, 2) By using a three-dimensional (3D) high-resolution diffusion-weighted imaging sequence (HR-DWI), image quality is improved and confers a 5-fold improvement in resolution when compared to standard two-dimensional (2D) DWI (S-DWI). This novel 3D DWI technique has been developed by our team and can be applied on existing 1.5T or 3T MRI systems. S-DWI suffers from two important limitations. a) It uses single-shot echo-planar imaging (EPI) for data acquisition, which produces magnetic susceptibility induced streaking artifacts and geometric distortions so that round objects may appear oval. b) The relatively low signal-to-noise ratio and 2D image acquisition with S-DWI limit spatial resolution, which is defined by the minimum distance between two objects required to resolve them uniquely. Our hrMRI incorporating HR-DWI overcomes these limitations by using magnetization prepared, multi-shot, turbo-spin-echo acquisition, which improves signal-to-noise ratio (SNR), spatial resolution, and image quality, and eliminates geometric distortions and streaking artifacts associated with EPI.

In a prospective study assessing the performance of hrMRI in 17 prostate cancer patients on active surveillance, the technique was shown to detect tumors not seen on standard mpMRI. Standard mpMRI predicted biopsy results (AUC 0.72, Fisher's exact $p < 0.001$), but high-resolution DWI sequences allowed MP-MRI to be more highly predictive of biopsy results (AUC 0.88, Fisher's exact $p < 0.001$). hrMRI had a sensitivity of 95.7% and identified tumor in 22 of 23 zones proven to have cancer on biopsy. In contrast, standard mpMRI had a sensitivity of 60.9% and only identified 14 of 23 biopsy-positive zones ($p = 0.004$). In all, hrMRI was shown to detect 60% of tumors not seen on standard MRI.

2.6 Fluciclovine and PET-MRI in Prostate Cancer

Positron emission tomography (PET) imaging has also been increasingly used for detection of occult distant metastases in patients with advanced prostate cancer using prostate-cancer-specific radiotracers (PSMA) or those that accumulate preferentially within prostate cancer tissue (11C choline, 11C acetate, and 18F fluciclovine). While PET technology is usually paired with CT imaging for 3D localization due to wide availability of CT technology, there have been efforts to pair PET technology with MRI to improve identification of lesions both within and outside of the prostate gland, given the advantages in spatial resolution of MRI over CT imaging. While mpMRI is a very sensitive imaging modality for identifying localized prostate cancers, its specificity is limited; co-localization of tumors identified on MRI with PET imaging may be able to improve specificity to account for this limitation.

18F-fluciclovine is a radiolabeled leucine (amino acid) analog that accumulates within prostate cancer, and early work has suggested that co-localization of this PET radiotracer with 3-D mpMRI imaging may enhance accuracy of localization of intraprostatic cancer lesions compared with mpMRI or PET/CT alone. In a study of 21 patients who underwent 18F-fluciclovine PET/CT and mpMRI prior to radical prostatectomy, combined 18F-

fluciclovine PET/CT and mpMRI imaging yielded a positive predictive value of 82% for tumor localization, which was significantly higher than that with either modality alone. This would suggest that pairing 18F-fluciclovine PET imaging with MRI directly may improve localization of cancers within the prostate for HIFU treatment planning. We hypothesize that further leveraging the sensitivity and spatial resolution of hrMRI with the specificity of PET imaging may further enhance performance in accurately identifying cancers within the prostate.

2.7 MR/US-Fusion for Targeting of Prostate Cancers

The advent of improved prostate imaging using multiparametric MRI and PET have dovetailed with advances in fusion software platforms that offer the ability to overlay static MRI images with real-time ultrasound images at the time of biopsy. This technology, called MR-US fusion, allows clinicians to target potential regions of interest in the prostate seen on mpMRI during an transrectal ultrasound-guided biopsy. Targeted MR-US fusion biopsies have been shown to significantly improve sensitivity and overall accuracy of biopsy over standard sextant biopsy by 24% and 14%, respectively. Most academic centers now offer MR-US fusion biopsies for patients with persistent rising PSA after negative standard biopsy and for surveillance biopsies while on active surveillance. MR-US fusion techniques are also being applied to focal ablation of prostate cancers with HIFU; both the Sonablate and Ablatheram HIFU platforms have announced partnerships with MR-US fusion companies to provide targeting during tumor ablation with HIFU. However, despite these improvements, the accuracy of targeted biopsy and targeted focal therapy is necessarily limited by accuracy of the MRI imaging for detection and localization of lesions.

2.8 Combining MR/US-Fusion, hrMRI, and PET-MRI with HIFU for Focal Treatment of Prostate Cancer

Because the oncological effectiveness of HIFU depends on robust mapping and targeting of lesions within the prostate, improved detection of lesions using hrMRI and/or PET-MRI could provide a significant advantage in HIFU cancer control outcomes. Patients who are eligible for hemigland and focal HIFU absolutely depend on imaging for treatment planning; for example, in a patient with an index lesion of the right side of the prostate only, if imaging fails to detect a small focus of prostate cancer present on the left, hemigland HIFU (only treating the right side of the prostate) will not be effective at eradicating the entire bulk of his disease. It is even more important to accurately identify all prostate cancers when mapping for true focal therapy, since only identified lesions are ablated. We have previously shown that hrMRI detects up to 60% of tumors within the prostate not seen on mpMRI, and PET-MRI techniques may be able to improve the accuracy of this detection. Even if lesions that are ignored by mpMRI but detected on PET-hrMRI are indolent, long-term growth of these lesions may certainly affect cancer control outcomes over time and require costly and morbid retreatment. We believe that improved imaging at the outset of focal therapy would provide more comprehensive eradication of cancer burden from the start, resulting in improved long-term outcomes.

3.0 STUDY DESIGN:

3.1 Overview

This prospective trial will evaluate the effectiveness of 18F-fluciclovine PET-hrMRI versus standard mpMRI at identifying prostate cancer targets for HIFU therapy. Patients with clinically localized, Gleason score 7-10 prostate cancer localized to one lobe on prior biopsies or overall Gleason score 6 with \geq half of systematic biopsy cores positive and \geq 50% of core involvement in at least one core, interested in HIFU would receive both a standard mpMRI and 18F-fluciclovine PET-hrMRI. They would then undergo a mapping biopsy using a standard sextant template plus MR/US-fusion targeted biopsy of any lesions with PI-RADS scores \geq 3 on hrMRI or 18F-fluciclovine PET positivity. The primary endpoint would assess the number of biopsy-proven cancers that mpMRI would have missed compared with hrMRI and/or 18F-fluciclovine PET. Following our tumor mapping study, patients with high grade disease (i.e. Gleason grade 4 or 5) in one lobe undergo hemigland or focal HIFU of that lobe. At 6 months, patients would undergo repeat mpMRI and prostate biopsy (MR/US-fusion biopsy plus standard sextant biopsy) to assess the negative biopsy rate in the treated region and absence of Gleason grade 4 or 5 in the untreated region as secondary endpoints

3.2 Study Population

The study population for recruitment will be patients within the academic urology practice at Cedars-Sinai Medical Center. After initial visit, any patient with clinically localized prostate adenocarcinoma with Gleason score 7-10 prostate cancer localized to one lobe on prior biopsy desiring therapy with HIFU may be considered a potential study participant. Subjects with newly diagnosed disease or on active surveillance may be considered.

3.2.1 Inclusion Criteria

1. Biopsy consisting of \geq 10 tissue cores sampled
2. PSA \leq 20 ng/mL (within 3 months of consent)
3. cT1-cT2c
4. Either overall Gleason score \geq 7 with Gleason grade 4 or 5 component localized to one lobe (i.e. right or left) OR overall Gleason score 6 with \geq half of systematic biopsy cores positive and \geq 50% of core involvement in at least one core
5. Patient considering focal HIFU therapy

3.2.2 Exclusion criteria:

1. Previous local therapy for prostate cancer
2. Inability to receive PET tracer
3. Inability to receive MRI
4. Suggestion of extracapsular extension or seminal vesicle invasion on imaging, if imaging was completed per SOC prior to or during screening
5. Estimated creatinine clearance $<$ 45 mL/min (Cockcroft-Gault equation)
6. Any other condition which, in the investigator's option, may make the patient a poor candidate for participation in a clinical trial.

3.3 Study endpoints

Primary Endpoint: To determine the number of biopsy-proven cancers that standard imaging would have missed compared with PET-hrMRI on mapping MRI

Secondary Endpoint: Negative biopsy rate on standard 12-core biopsy 6 months following HIFU therapy.

Exploratory Endpoint: RNAseq transcriptome analysis of lesions that are positive on mapping biopsy.

3.4 Study Procedures

3.4.1 Screening/Baseline Procedures

Subjects will be identified by study investigators within the academic urology practice at Cedars-Sinai Medical Center during routine clinical practice. All study assessments for eligibility are performed as part of standard of care. Once a patient has been diagnosed, expressed interest in HIFU, and recommended study participation, they will be presented with the Informed Consent Form, including a description of the study purpose, risks, benefits and possible alternatives. The prospective participant will be given sufficient time to consider participation in the research. Patients will be asked to sign the study consent form after receiving a complete explanation of the study.

This study will enroll patients with clinically localized, Gleason score 7-10 prostate cancer localized to one lobe on prior biopsies or overall Gleason score 6 with \geq half of systematic biopsy cores positive and \geq 50% of core involvement in at least one core, interested in HIFU as primary treatment. Patients with low Gleason grade cancer (e.g. Gleason grade 3) on the contralateral lobe are allowed since the standard-of-care for such low grade disease is observation. Patients with very low risk disease and low-volume, low-risk disease are excluded since their preferred management is active surveillance. Patients will present with newly diagnosed disease or after a period of active surveillance. If there is suggestion of extracapsular disease or seminal vesicle involvement on MRI, these patients will be excluded. Metastatic workup with cross sectional imaging and/or bone scan will not be mandatory, since they are not indicated for low- and intermediate-risk prostate cancers according to AUA and NCCN guidelines.

Screening procedures include:

3.4.1.1 Informed Consent

Informed consent must be obtained prior to any protocol assessment or procedure which is not performed as part of local routine care. Subjects must also grant permission to use protected health information per the Health Insurance Portability and Accountability Act (HIPAA). Signed and dated ICF and HIPAA for enrolled participants who are not subsequently screened or undergo study intervention will be maintained at the study site.

3.4.1.2 Medical history

Medical history (comorbidities) includes clinically significant diseases that are currently active or that were active, including past surgical history, medications, social history,

family history including history of prostate cancer, dates of previous prostate biopsies, prostate biopsy pathology results, PSA results, dates and results of previous prostate imaging

3.4.1.3 Reporting on Concomitant medication

Any current concomitant medications and treatments will be recorded

3.4.1.4 Demographics

Age, ethnicity/race

3.4.1.5 Review subject eligibility criteria

All necessary procedures and evaluations must be performed to document that the subject meets all of the inclusion and none of the exclusion criteria.

3.4.1.6 Physical exam including vital signs, height, and weight

Physician directed physical exam. This may be collected within 90 days of screening.

3.4.1.7 Adverse event assessment

Adverse events will be assessed at imaging, post imaging (biopsy), HIFU, and HIFU follow up. See section 5.1 and 5.2 for Adverse Event and reporting. Only grade 3 and above imaging-related AEs will be captured and all SAEs following the receipt of fluciclovine F18.

3.4.2 Study Calendar

Procedure	Screening	Imaging	Post-imaging²	Standard of Care (SOC) Treatment	Post SOC Treatment 6 months (+/- 1.5 months) following HIFU
Informed Consent/Registration	X				
Demographics/Medical History	X				
Prior and Current Medication Review	X				
Vital Signs ⁵	X				
Physical Exam ⁵	X				
Symptoms Assessment	X				
Standard MRI		X (at least one day prior to targeted prostate biopsy)			X (at least one day prior to targeted prostate biopsy)
			X		X

Tissue collection ⁴					
18-fluciclovine PET-hrMRI		X (at least one day prior to targeted prostate biopsy)			
Adverse Event Review ⁶		X	X	X	X
Hemigland or Focal HIFU ¹				X (performed within 4 months after mapping and/or targeted prostate biopsy)	
Standard Sextant Mapping Biopsy			X		X
MR/US-fusion targeted biopsy			X ³		X

1. Focal HIFU performed on study for patients with confirmed unilateral high grade prostate cancer.
2. End of study for bilateral Gleason ≥ 7 disease
3. Of any lesions with PI-RADS scores ≥ 3 on hr MRI or 18F-fluciclovine PET positivity
4. Tissue collection includes left over tissue from standard of care collection only.
5. Do not need to be repeated if obtained within 90 days of screening.
6. Only grade 3 and above imaging-related AEs will be captured and all SAEs following the receipt of fluciclovine F18.

Pre-HIFU Imaging Protocol for Tumor Mapping

Eligible participants will then undergo mapping MRI in advance of HIFU therapy using both standard mpMRI and PET-hrMRI. All imaging will be completed in one sitting. hrMRI increases the length of the MRI by approximately 5 minutes. PET-MRI sequences increased the length of mpMRI by 30 minutes. Scanning will be done on the Siemens Biograph mMR scanner at the Research Imaging Core facility in the Davis Building.

Subjects undergoing a PET-hrMRI will be screened using the standard clinical protocol to determine whether it is safe to administer contrast to the subject.

PET scans involve injection of a radioisotope. Subjects undergoing a contrast-enhanced MR-PET will be screened using the standard clinical protocol to determine whether it is safe to administer contrast to the subject. An IV line will be inserted, and the participant will receive 10 mCi $\pm 20\%$ 18F-fluciclovine injection diluted up to 10mL injected via the IV, as an IV bolus injection followed by 10mL flush with normal saline solution. The participant will then be positioned supine in the scanner and will be scanned in the area of the prostate. The research PET scan will be a dynamic list mode scan. Meaning the PET would start first, then 18F fluciclovine would be injected immediately after the scan is started. For the PET acquisition, participants will be imaged for approximately 30 minutes.

All MRI images will be read according to PI-RADS (version 2) by a dedicated GU radiologists who has experience reading over 500 prostate MRIs. All PET scans will be

read by nuclear medicine co-investigators on the study ([name]). All lesions with PI-RADS greater than or equal to 3 and all PET positive areas will be considered suspicious for cancer. A region of interest (ROI) application will be used. The circumference of a suspicious lesion will be drawn on each individual MRI slice. The lesion volume and average ADC will be calculated from the ROI's. The tumor volumes and ADCs will be provided by the radiologist. To prevent the hrMRI from influencing the review of the mpMRI, all mpMRI's will be reviewed first. The radiologist will always be blinded to previous pathology.

Mapping Biopsy Protocols

After the pre-HIFU imaging protocol for tumor mapping, all patients will undergo a transrectal ultrasound-guided targeted mapping biopsy. The biopsy will include a standard sextant template plus MR/US-fusion targeted biopsy of any lesions with PI-RADS scores ≥ 3 on hrMRI or 18F-fluciclovine PET positivity. These areas will be targeted using the UroNav targeting software platform. As an exploratory analysis, remnant formalin-fixed paraffin embedded tumor tissue will be requested for RNAseq transcriptome analysis of lesions that are positive on mapping biopsy.

Eligibility for HIFU

If subjects are found to have unilateral high grade disease (i.e. Gleason grade 4 or 5), they will be considered as a candidate for hemigland or focal HIFU therapy. Clinician judgment may be exercised in determining eligibility for HIFU, since established criteria based on volume and extent of disease do not exist. If patients have high grade disease in both lobes, they will not be eligible for HIFU therapy on this trial. Their data will be used to assess the primary endpoint but they will not be considered for secondary endpoints.

HIFU Therapy and Follow Up Schedule

Patients who are eligible for HIFU will receive hemigland or focal HIFU per standard-of-care. All subjects will receive repeat mpMRI and MR/US-guided biopsy of all positive sites + systematic 12-core prostate biopsy at 6 months (or as clinically indicated). As an exploratory analysis, remnant formalin-fixed paraffin embedded tumor tissue will be requested for RNAseq transcriptome analysis of lesions that are positive on biopsy.

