1.0 STUDY ABSTRACT

The arrival of High-Intensity Focused Ultrasound (HIFU) technology along with advances in prostate imaging may make focal gland ablation feasible. While the mainstays of therapy for clinically localized prostate cancer, surgery and radiation therapy, induce significant morbidity such as urinary incontinence, erectile dysfunction, and bowel dysfunction due to bystander effects of whole-gland treatment, HIFU permits focal destruction of prostate cancers, which has the potential to minimize these morbidities and maximize quality of life. Advances in prostate MRI allow the majority of high grade cancers to be detected. Software platforms exist that enable real-time fusion of prostate MRI images with ultrasound, which allows for targeting of prostate lesions found on MRI during transrectal biopsy. The confluence of all of this technology—HIFU, multiparametric MRI (mpMRI), and MR/US-fusion targeting—creates the possibility of highly targeted focal ablation of prostate cancers. Nonrandomized clinical trials of hemigland and focal ablation with HIFU in Europe have shown promising trilecta rates—cancer control, potency, & continence—up to 1y post-treatment.

While early results of HIFU therapy for clinically localized prostate cancer are promising, the effectiveness of HIFU therapy will ultimately be limited by the accuracy of prostate cancer imaging. Because prostate cancer is often multifocal, identification of all clinically relevant prostate cancer lesions is critical to complete treatment of the disease, whether it is hemigland or true focal ablation. Modern mpMRI is unable to detect 20% of high-grade cancer and approximately 50% of low-grade cancers. To address this shortcoming, our team at Cedars-Sinai has developed high-resolution prostate MRI (hrMRI) technology that improves resolution 5-fold compared with standard multiparametric MRI. (1) High-resolution imaging has been shown to detect 60% of tumors not seen on standard MRI.(2) Pairing this technology with PET may allow highly specific targeting for focal therapy. Because the oncological effectiveness of focal therapy depends on robust targeting, PET-hrMRI could provide a significant advantage in cancer control outcomes for HIFU.

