6.0 Statistical Analysis

Primary Endpoint: To compare the number of biopsy-proven cancers that standard imaging would have missed compared with PET-hrMRI on mapping MRI (i.e. comparison of sensitivity of PET-hrMRI with mpMRI with biopsy-proven cancer as the gold standard).

Our preliminary data suggests that up to 60% of tumors invisible to standard mpMRI are detected on hrMRI. It is unclear how many additional lesions will be identified on fluciclovine PET-MRI. Since all areas of concern will be biopsied and only biopsy-proven tumors will be treated with HIFU, the morbidity of the surgical intervention is minimized and its potential to achieve cure is maximized.

Power Assessment: The power for the McNemar's type test proposed by Durkalski et al. (2003) is evaluated based on four correlations: r1: between lesions evaluated by PET-hrMRI for the same patient, r2: between lesions evaluated by mpMRI for the same patient, r3: between evaluations PET-hrMRI and mpMRI for the same lesion and r4: between evaluations PET-hrMRI and mpMRI for the different lesions at the same patient. In this way, we define four scenarios of correlation among lesions: (a) no correlation ($r1 = r2 = r4 = 0, r3 = 0.15$), (b) low correlation ($r1 = r2 = 0.1, r3 = 0.15, r4 = 0.015$), (c) medium correlation ($r1 = r2 = 0.4, r3 = 0.15, r4 = 0.06$) and (d) high correlation ($r1 = r2 = 0.8, r3 = 0.15, r4 = 0.12$). In addition, the number of lesions for each patient is defined as equal to 1 - 2 on average from preliminary data.

The minimum sample size to reach 80% of power is 22 patients when each patient has exactly 1 lesion (total of 22 lesions); 19 patients when the average number of lesions is 1.35 (total of 26 lesions); and 17 patients when the average number of lesions is 2 (total of 34 lesions). Given that our estimated number of biopsy-proven lesions per patient will be 1–2 based on historical data, we will proceed with a sample size of 20 patients.

Statistical Analysis: Sensitivities will be compared using McNemar's type test proposed by Durkalski et al. (2003) for cluster matched binary data. In addition, the 95% confidence interval for difference between sensitivities will be calculated as proposed by Yang et al. (2012).

Secondary Endpoints: Negative biopsy rate within treatment zones on standard 12-core biopsy 6 months following HIFU therapy; rate of high grade cancer in the untreated lobe.

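### The plan tests PET and hrMRI only as one composite, so it does not report which of them produced a gain or how many benign targets it cost, and blinding to prior pathology is not stated for the PET readers

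*Combined protocol and SAP*

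**What the plan says.** **Scoring rule.** Under the tumor-mapping imaging protocol in section 3.4.2, "All lesions with PI-RADS greater than or equal to 3 and all PET positive areas will be considered suspicious for cancer". The study calendar footnote and the mapping biopsy paragraph use the same either/or rule to choose targets. Section 3.1 carries it into the endpoint: "The primary endpoint would assess the number of biopsy-proven cancers that mpMRI would have missed compared with hrMRI and/or 18F-fluciclovine PET".

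**Analysis.** Section 6.0 defines the primary comparison as a "comparison of sensitivity of PET-hrMRI with mpMRI with biopsy-proven cancer as the gold standard". It uses a McNemar-type test for clustered pairs and a 95% confidence interval for the difference in sensitivities. The remaining endpoints in sections 3.3 and 6.0 are biopsy results after HIFU and exploratory RNAseq.

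**Role of PET.** Two purposes are given. Section 2.8 expects more lesions to be found: "improved detection of lesions using hrMRI and/or PET-MRI could provide a significant advantage in HIFU cancer control outcomes". Section 2.6 expects better specificity: "co-localization of tumors identified on MRI with PET imaging may be able to improve specificity to account for this limitation". On the size of the PET contribution section 6.0 says "It is unclear how many additional lesions will be identified on fluciclovine PET-MRI".

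**Readers.** Section 3.4.2 has mpMRI read before hrMRI and blinds the radiologist to earlier pathology. PET is read by nuclear medicine co-investigators. For them the section gives no blinding, no place in the reading order and no threshold for calling PET positive.

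**The concern.** Under an either/or rule, an added PET call can raise the composite's sensitivity or leave it unchanged, but never lower it. Sensitivity is computed among proven cancers only, so a PET call on benign tissue costs nothing in the analysis. A significant result could therefore come from hrMRI alone, from informative PET, or from PET that flags a large share of the gland. The planned output would look the same in each case.

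The distinction matters because the components differ in burden. By sections 3.4.2 and 4.0, hrMRI adds about 5 minutes, whereas PET adds about 30 minutes, a tracer injection and 8 mSv. A centre reading the result will want to know whether PET was needed.

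The reader question bears on the same comparison. Every man enters with known biopsy results, often with high-grade disease in one lobe. A PET reader aware of that lobe could call it more readily, and PET calls help PET-hrMRI only.

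**Working it through.** **Inputs.** Study Summary: 35% of proven tumors seen on PET-hrMRI only, 0% on mpMRI only, alpha 0.05, n = 20, power 80%. Section 2.5 pilot (no PET, counted by zone): hrMRI 22/23, mpMRI 14/23. Miss rates for mpMRI: 9/23 = 39.1% from the pilot, and 20% for high-grade disease from section 1.0 ("Modern mpMRI is unable to detect 20% of high-grade cancer and approximately 50% of low-grade cancers").

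**1. The plan's figure.** For one-way discordance p, two-sided, n = (1.96·√p + 0.8416·√(p − p²))² / p². With p = 0.35: (1.1595 + 0.4014)² / 0.1225 = 19.89, so 20. Power at 20 is 0.803. The stated figure reproduces.

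**2. PET adds nothing, hrMRI repeats its pilot.** p = 22/23 − 14/23 = 8/23 = 0.348. Power at 20 is Φ[(0.348·√20 − 1.96·√0.348) / √(0.348 − 0.121)] = 0.799. An exact two-sided test (six or more one-way discordant lesions) gives 0.748, against 0.755 at p = 0.35.

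A lower reading of the pilot is possible, because sections 2.5 and 6.0 also say that hrMRI detects up to 60% of tumors missed by mpMRI. Then p = 0.6 × 0.391 = 0.235, and the same formula gives power of about 0.59.

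**3. Room left for PET.** If hrMRI reaches 22/23, PET can add at most 1/23 = 4.3%. Testing that gain against hrMRI would need about 179 lesions by the formula in step 1. The plan foresees 1 to 2 per man in 20 men, so PET's increment can only be described here.

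**4. Conditional illustration: uninformative PET.** Assume PET flags a random share q of the gland, hrMRI adds nothing, every missed tumor in a flagged area is found, lesions are independent, and no tumor is seen on mpMRI alone. A lesion is then one-way discordant with probability m·q, where m is the mpMRI miss rate. The large-sample clustered statistic is (Σ b_k/n_k)² / Σ (b_k/n_k)², where man k has n_k lesions, b_k of them discordant; it rejects above 3.84. With one lesion per man it equals the number of discordant lesions, so four suffice. Chance of significance with 20 / 27 / 40 lesions in 20 men:

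| q | m = 39.1% | m = 20% |
|---|---|---|
| 10% | 0.7% / 0.4% / 6% | 0.1% / 0.0% / 0.7% |
| 25% | 13% / 12% / 49% | 2% / 1% / 12% |
| 50% | 57% / 61% / 93% | 13% / 12% / 50% |

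These figures are sensitive to the assumptions:

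- If half of the missed tumors in flagged areas are found, the q = 50% row becomes the q = 25% row (0.391 × 0.5 × 0.5 = 0.098).
- Under the exact six-or-more rule, the 57% for 20 single lesions becomes 18%. That rule fits section 6.0's 22 patients with one lesion each (power 0.837) better than the four-lesion rule, which gives 96% power at p = 0.35 with only 20.
- If hrMRI repeats its pilot (27 lesions, m = 39.1%), q = 0 / 25% / 50% gives 97.5% / 98.1% / 98.5%, so PET hardly matters.

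No document gives q.

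**5. Planned outputs.** Across sections 3.1, 3.3 and 6.0 there is no PPV, no count of benign targets, no hrMRI-alone comparison, and no split of MRI-positive targets by PET result. The last is what section 2.6's specificity expectation would need.

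**The case against.** The stated objective concerns the two technologies together. The study imaging is defined as the combination, and attributing a gain to PET is not a declared aim. Comparing sensitivity is a reasonable choice when finding missed lesions is the purpose, and the consequence of a false PET call is limited, because in section 6.0's words "Since all areas of concern will be biopsied and only biopsy-proven tumors will be treated with HIFU". A false call leads to extra cores, not to ablation. All of this stands, and it is why the primary test should not change.

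It can also be said that the component analyses could be run later. That is partly true: the targets are biopsied anyway, so yield and hrMRI-alone sensitivity can be derived if someone records which read flagged each target. The PET readers' blinding and positivity rule cannot be supplied after the reads.

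Three stronger readings are tempting, and the documents support none of them:

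- **That the primary test is invalid or gives false positives.** A gain in the composite's sensitivity would be a real gain, since every counted cancer is biopsy-proven.
- **That the PET readers know the prior pathology.** The plan does not say so; it omits the point.
- **That useless PET would probably carry the trial.** The high percentages in step 4 need no hrMRI gain, contrary to the pilot, together with a q of 25% to 50% that no document gives.

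**Conclusion.** The concern holds as a limit on interpretation. The planned test answers whether PET plus hrMRI finds more proven cancer than mpMRI. It does not report which component did so, or the cost in benign targets.

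The main evidence on size is the match between the pilot hrMRI gain (34.8%) and the powered effect (35%). If the pilot counts carry over from zones to lesions, a positive result is expected with power of about 80% even when PET contributes nothing. On the lower reading (60% of missed tumors) that power is about 59%. The uninformative-PET figures are only a conditional illustration, and the effect is negligible if hrMRI repeats its pilot.

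A reader might infer that the data could never separate the components. That goes too far: the separation is not planned, and it is feasible descriptively. The missing blinding statement for PET readers is an omission whose effect cannot be sized from the documents, but any bias would favor one side only. The point is worth acting on because the remedy is cheap and part of it must precede the first read.

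**What to change.** 1. **Section 3.4.2, readers.** Extend blinding to previous pathology to the PET readers, and have them fix one PET-positivity rule before the first read. Whether PET is read with or without the MRI can stay the investigators' choice. Reading it without would change the index test and may lose sensitivity.
2. **Data collection.** Record for each target which read flagged it: mpMRI, hrMRI, PET.
3. **Section 6.0, supporting analysis.** Compare hrMRI alone with mpMRI on the same proven lesions, by the same clustered test.
4. **Section 6.0, descriptive.** Report PPV and benign targets per man for three groups: hrMRI-positive/PET-positive, hrMRI-positive/PET-negative, and PET-only. Give 95% intervals that allow for clustering within men. The first two groups address the specificity expectation in section 2.6.
5. **Conclusions.** Limit statements about PET to items 3 and 4. Leave the primary test as it is.

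**Cost.** A few sentences, one data field per target and two added analyses, with no extra scan, core or patient, since these targets are already biopsied. The drawback is precision. At a PPV of 50%, the exact 95% interval is about 19% to 81% with 10 PET-only targets and 27% to 73% with 20, and clustering widens both. The target counts are assumptions.
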